#### 4.10.3 Deaths and Serious Adverse Events

The following summaries will be provided by actual treatment group at the time of the event:

- Number and percentage of subjects reporting a serious AE by SOC and PT
- Number and percentage of subjects reporting a serious AE by relationship to study treatment
- Number and percentage of AEs leading to death by relationship to study medication
- Exposure-adjusted (patient years) serious adverse events by treatment group, where the total number of subjects for each column includes all subjects who took the dose at least once during the study. The exposure-adjusted rate divides the total number of serious AEs attributed to each dose by duration of exposure (in years) to that dose. The duration for subjects who complete the study on their randomised dose is (date of last dose – date of first dose + 1). For subjects who escape, duration is based on treatment periods defined in Section 4.2.

The following listings will be provided:

- A by-subject listing of all Serious AEs
- A by-subject listing of all AEs leading to discontinuation of study treatment
- A by-subject listing of all Serious AEs leading to death

#### 4.10.4 Disease-related Events

Disease-related Events (DREs) will be summarised in alphabetical order by actual treatment group at the time of the event. A by-subject listing of all DREs that occurred during the study will also be provided.

#### 4.10.5 Respiratory Events

Numbers and percentages of subjects experiencing persistent cough, or persistent dyspnea or persistent DLCO decrease will be reported in a table by actual treatment group at the start time of the event.

Event	Definition
Persistent cough	Cough grade 2 or greater recorded for 3 consecutive weeks (15 or more days) on the eCRF page.
Persistent dyspnea	Borg Scale grade 3 or greater recorded for 3 consecutive weeks (15 or more days) on the eCRF page.
Persistent decrease of D LCO by >15%	Relative decrease of DLCOHCPP of $\geq 15\%$ compared to Baseline for 3 consecutive weeks (15 or more days)

These definitions are provided for guidance to identify potential cases. Final adjudication will be conducted by the SRT.

#### 4.10.6 Cardiovascular Events

Occurrences of the below cardiovascular events will be listed in 9 separate listings:

- Arrhythmias
- Congestive heart failure
- Cerebrovascular event stroke and transient ischemic attack
- Deep vein thrombosis/ Pulmonary embolism
- Myocardial Infarction / Unstable Angina
- Peripheral arterial thromboembolism
- Pulmonary Hypertension
- Revascularisation
- Valvulopathy

All relevant data captured in the CRF will be listed. However, as only very few events might occur during the conduct of the study, the design of the listings might be adapted to the actual observed data.

#### 4.10.7 Liver Events

Liver chemistry stopping events as defined in the protocol trigger further assessments (e.g. liver PK sampling, assessment of alcohol intake, liver biopsy...).

All relevant data captured in the CRF will be listed. However, as only very few events might occur during the conduct of the study, the design of the listings might be adapted to the actual observed data.

#### 4.10.8 Clinical Laboratory Evaluation

Hematology and biochemistry samples will be taken at Screening, Baseline, Weeks 1, 2, 4, 8, 12, 16, 20, 24, 32, 36, 42, 52, at follow-up visit and at a potential early withdrawal visit.

Urinalysis will be taken at Screening, Weeks 4, 8, 12, 16, 20, 24, 32, 42, 52, at follow-up visit and at a potential early withdrawal visit.

The central laboratory will analyse and assess blood and urine samples for the following:

**Table 8 Laboratory Assessments**

Hematology	Biochemistry	Urinalysis
Hemoglobin	Sodium	Urine dipstick
Hematocrit	Potassium	Glucose
Mean cell volume (MCV)	Calcium	Protein
Mean corpuscular hemoglobin (MCH)	Phosphate	Creatinine
Mean corpuscular hemoglobin concentration (MCHC)	Urea	
Erythrocyte mean corpuscular Volume	Creatinine	Microscopy of urine sediment for erythrocytes, leukocytes and casts if urine dipstick abnormal
Erythrocyte count	Creatinine clearance (calculated)	
Reticulocyte count	Aspartate transaminase (AST)	
Leukocyte count	Alanine transaminase (ALT)	
Leukocyte differential count	γ-glutamyl transpeptidase (GGT)	
neutrophils	Lactate dehydrogenase (LDH)	
eosinophils	Alkaline phosphatase (AP)	
basophils	Bilirubin (total)	
monocytes	Creatine Phosphokinase (CPK)	
lymphocytes	Total protein	
Platelets	Albumin	
Activated partial thromboplastin time (aPTT)	Albumin/globulin ratio	
Prothrombin Time (PT)	Serum Glucose	
International Normalised Ratio (INR)	C-reactive protein (CRP)	
Fibrinogen	Cholesterol	
Erythrocyte Sedimentation Rate (ESR)*	Triglycerides	
	High-density lipoprotein (HDL)	
	Low-density lipoprotein (LDL)	

\*Measured locally

Descriptive statistics for observed values and change from baseline will be presented by treatment for each visit and for all parameters for hematology, biochemistry and urinalysis, separately. Estradiol, follicle stimulating hormone and rheumatoid factor will be assessed only at Baseline and will be listed.

Laboratory values reported below the limit of quantification (BLQ) will be replaced by one-half the limit of quantification when reporting summary statistics.

Laboratory parameters of interest will be summarised (number and percentages) by time point and by grade as defined in [Appendix B](#).

A summary of shift from baseline to worst grade during the study value will be provided for specific laboratory parameters of interest from [Appendix B](#) to be identified in the final version of this analysis plan.

Boxplots will be produced to display the distribution of results for laboratory parameters of interest by time point and by actual treatment group; these parameters are specified in [Appendix B](#).

Separate by-subject listings of laboratory data for hematology, biochemistry and urinalysis will be provided by randomised treatment group, with abnormal values highlighted, and including center, subject identifier, age, sex, race, weight and visit. For each subject, all results for any lab parameter that has at least one abnormal value will be included in the listing. Laboratory reference ranges (Lower Limit of Normal, upper Limit of Normal) will be presented for each laboratory parameter.

#### **4.10.9 Pulmonary assessments**

All pulmonary assessment results (chest X-ray, cough, Borg dyspnea questionnaire, chest auscultation, pulmonary function tests (PFTs - spirometry, gas transfer [ $D_{LCO}$ ]) and pulse oximetry) will be provided in listings.

Summary statistics will be provided for the change from baseline for the Borg dyspnea score, for pulmonary function tests, spirometry and  $D_{LCO}$ , and for pulse oximetry by visit. The number and percentages of subjects having a cough for each grade will be summarised by visit, in addition to the number and percentages of subjects having a relative decrease in  $D_{LCO}$  Hemoglobin-corrected Percent of Predicted (DLCOHCPP) of >15% from baseline.

A subject's baseline DLCOHCPP value will be taken as the lowest value obtained from the Screening or Day 1 assessment, or any unscheduled visit in between. For rescreened subjects, only the last available Screening assessment will be considered.

The same visit that has been determined to provide the baseline value of DLCOHCPP will be used to provide the baseline value for all other pulmonary function test parameters (including DLCO Absolute Value, HGB corrected DLCO, FEV1, FVC, FEV1/FVC, percent predicted FEV1, percent predicted FVC, predicted FEV1, predicted FVC).

For summary tables, reporting of subjects with >15% decrease from baseline will be shown separately for subjects with current DLCO <70%. A separate summary will be provided by baseline DLCO value (<70% and ≥70%).

Individual patient profiles of DLCO over time will be shown in a figure by randomised treatment group.

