### 5.1. Inclusion Criteria

A subject will be eligible for inclusion in this study only if all of the following criteria apply:

Subjects eligible for enrolment in the study must meet *all* of the following criteria:

[1] AGE
1. Age $\geq 18$ years at the time of signing informed consent.
[2] TYPE OF SUBJECT AND DIAGNOSIS INCLUDING DISEASE SEVERITY
2. Meets ACR/EULAR 2010 RA Classification Criteria. 3. Functional class I, II or III defined by the 1992 ACR Classification of Functional Status in RA. 4. Disease duration of $\geq 12$ weeks (time from onset of patient-reported symptoms of either pain or stiffness or swelling in hands, feet or wrists). 5. Swollen joint count of $\geq 4$ (66-joint count) and tender joint count of $\geq 4$ (68-joint count) at screening and at Day 1. 6. DAS28(CRP) $\geq 3.2$ at screening and DAS28(ESR) $\geq 3.2$ at Day 1.

- 7. C-Reactive Protein (CRP)  $\geq 5.0$  mg/L at screening.
- 8. Must have previously received MTX (15-25 mg weekly) for at least 12 weeks before screening, with no change in route of administration, with a stable and tolerated dose for  $\geq 4$  weeks prior to Day 1. A stable dose of MTX  $\geq 7.5$  mg/week is acceptable, if the MTX dose has been reduced for reasons of documented intolerance to MTX, e.g. hepatic or hematologic toxicity, or per local requirement.

[3] WEIGHT

- 9. Weight  $\geq 45$  kg.

[4] SEX

- 10. Male or female subjects are eligible to participate so long as they meet and agree to abide by the contraceptive criteria detailed in [Appendix 12.2](#).

[5] INFORMED CONSENT

- 11. Written informed consent prior to any of the screening procedures including discontinuation of prohibited medications.

[6] OTHER SAFETY-RELATED

- 12. Willing to continue or initiate treatment with oral folic acid (at least 5 mg/week) or equivalent and be treated during the entire study (mandatory co-medication for MTX treatment).
- 13. Diffusing capacity of the lung for carbon monoxide ( $D_{LCO}$ )  $\geq 60\%^{a,b}$  predicted; forced expiratory volume in 1 second (FEV1)  $\geq 70\%$  predicted.
  - a Screening and Day 1 values within 10% of each other (the test may be repeated twice within the screening period, *i.e.* subjects may undergo a total of three  $D_{LCO}$  tests during the screening period).

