### 4.2 General Presentation Considerations

For each subject 'Baseline' is defined as the last available assessment prior to the start of study treatment. For Efficacy variables no Screening information will be used for Baseline. For DLCO, separate Baseline rules are defined in section 4.10.9. For each subject 'End of Study' is defined as the last available assessment which is on or after the day of last study treatment.

The relative study day will be included in adverse event data, medical history and concomitant medication listings, and will be calculated as follows:

- Relative Day 1 is the date of first study medication administration.
- Relative Day of date X = date X - Date of first study medication administration + 1 if date X is on or after date of first study medication administration.
- Relative Day of date X = date X - Date of first study medication administration if date X is before date of first study medication administration.

Relative days before first study medication administration will have the prefix “-“. Additionally for relative days after last study medication administration, the number of days since last study medication administration will be presented with the prefix “+“. Calculations of “Relative Day” will not include partial dates, but will be left blank in listings.

According to the design the study can be split into 5 time periods:

- Baseline to <Week 14: Day of first study medication administration up to and including the day before Week 14 study medication administration
- Week 14 to <Week 26 visit
- Week 26 to <Week 38 visit
- Week 38 to <Week 52 visit
- Safety Period: Week 52 visit to end of study

Safety period includes Week 52 and all later visits. All other periods start with (and include) Baseline visit or Week 14/26/38 visit and end with the day before the next period starts. Start of a new period is always the day of study medication administration. Safety Period starts with the Week 52 Visit. If the Week 52 visit is missing, Safety Period starts 14 days after the last study drug administration of the previous period.

If the Week 14/26/38 visit is missing, the day of the next non-missing visit will be the first day of the new period. For example, if the Week 14 visit was missed but the Week 16 visit was

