#### **4.10.11 Safety Monitoring**

##### **4.10.11.1 Data Review Committee**

A DRC (consisting of external rheumatology, infectious disease and respiratory experts, and GSK study team members that have no involvement in the acquisition of the data or direct contact with sites) will review ongoing unblinded safety data from the study and unblinded efficacy data at the interim analyses.

The first DRC review of safety data will be conducted after approximately 10 subjects per arm have completed 5 weeks of treatment, and subsequent reviews will take place approximately every 12 weeks thereafter until the end of the study.

Output shells for DRC outputs are provided in a separate document and the following outputs will be produced for each DRC review:

- Summary of Withdrawals by Reason for Withdrawal
- Summary of Demography Characteristics – Age, Gender and Weight
- Concomitant Medication
- Concomitant Medication of subjects with serious infections
- Concomitant Medication of subjects with DLCO Hemoglobin-corrected Percent of Predicted decrease  $>15\%$  change from baseline
- Summary of Treatment Emergent AEs - Overview
- Summary of Treatment Emergent AEs by SOC and PT
- Summary of AEs Leading to Withdrawal
- Plot of Most Common Adverse Events and Relative Risk
- Summary of SAEs
- Summary of AESIs of Serious Infections, Opportunistic Infections, Neutropenia, and PAP
- Summary of Hypersensitivity and Injection Site Reactions
- Summary of persistent cough, dyspnea or DLCO decrease
- Summary of Change from Baseline in DLCO Hemoglobin-corrected Percent of Predicted
- Summary of Proportion of Subjects with a  $>15\%$  Decrease from Baseline in DLCO Hemoglobin-corrected Percent of Predicted

- Summary Statistics of Haematology and Clinical Chemistry Values at Each Visit
- Distribution of Haemoglobin, Total WBCs, Neutrophil Counts, Platelet Counts, ALT, AST and Total Bilirubin by Visit and Treatment with Maximum over Time

For the interim efficacy analyses (when 90 subjects have completed 4 and 12 weeks of treatment) the time interval between subsequent reviews may deviate from the 12 weeks to combine these interim analyses with a safety review.

The decision to stop the study or randomisation to specific arms will be made by the DRC. Further details are given in the earlier sections of this RAP and will be included in the DRC Statistical Guidance document.

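### Taking the lowest pre-dose DLCO as baseline shifts mean change upward and lowers the >15% fall counts; the mean of the pre-dose tests would not

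*SAP*

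**What the plan says.** SAP 4.2 gives the general rule: baseline "is defined as the last available assessment prior to the start of study treatment". It then makes an exception: "For DLCO, separate Baseline rules are defined in section 4.10.9". For DLCO, section 4.10.9 states: "baseline DLCOHCPP value will be taken as the lowest value obtained from the Screening or Day 1 assessment". Tests done between those two visits are eligible as well. The visit that supplies this lowest value also supplies the baseline for FEV1, FVC and the other pulmonary function parameters. No reason is given for the exception, and no display against another baseline is planned.

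Protocol 5.1, criterion 13, requires "Screening and Day 1 values within 10% of each other" and adds that "the test may be repeated twice within the screening period". A subject can therefore have two or three pre-dose values.

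SAP 4.10.9 tabulates change from baseline and, by visit, subjects with a relative fall above 15%. The Data Review Committee (DRC) outputs in 4.10.11.1 include a "Summary of Change from Baseline in DLCO Hemoglobin-corrected Percent of Predicted", a >15% table and a persistence summary. The persistent-decrease event is defined in 4.10.5. Neither 4.10.5 nor 4.10.11.1 names another DLCO baseline. The protocol's AESI definition (4.7.1) and its treatment-interruption criterion (5.5.1) refer to baseline without defining it.

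**The concern.** A minimum is not a neutral summary of repeated measurements. Each DLCO test carries error, and choosing the lowest selects negative error. The next test regresses upward, so a subject whose lungs have not changed appears to improve, and one whose DLCO has fallen appears to have fallen less. The more pre-dose tests a subject has, the stronger the effect, so retested subjects become harder to flag.

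Protocol 5.3.2.2 adds to this. It lets a low Day 1 value be repeated and lets the visit proceed if the repeat is at least 70% predicted. Read literally, the SAP rule still makes the earlier low value the baseline. That section describes repeating DLCO only, so the visit with the lowest DLCO may have no spirometry, and the SAP gives no fallback for the other parameters.

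Incidence of pulmonary events is a major secondary safety endpoint, and DLCO monitoring is one of the protocol's named mitigations for pulmonary alveolar proteinosis. These tables are where a modest shift in DLCO would be looked for.

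**Working it through.** The plan states no power or event rate for DLCO, so there is no figure of its own to reproduce.

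**1. Direction (no assumptions).** The minimum is never above Day 1, so 0.85 × minimum ≤ 0.85 × Day 1. Every fall of more than 15% from the minimum is also one from Day 1; the reverse does not hold.

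**2. Limits set by the 10% agreement rule.** The protocol does not say whether 10% is relative or in percentage points.
- Relative: Screening 90, Day 1 100. The cut-off is 0.85 × 90 = 76.5, which is a 23.5% fall from Day 1.
- Points: Screening 60, Day 1 70. The cut-off is 0.85 × 60 = 51, and 1 − 51/70 = 27.1%.
- Example near the limit: Screening 80, Day 1 88, later 70. Then 70/88 − 1 = −20.5%, but 70/80 − 1 = −12.5%, which is not counted.

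**3. Expected bias.** With within-subject SD s, the expected minimum lies 0.56s below the true level for two tests and 0.85s below for three, before the agreement rule trims large differences. At s = 5% this is 0.56 × 5 = 2.8% and 0.85 × 5 = 4.25%. After trimming, simulation gives 2.1% and 3.7%.

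**4. Simulation.** Assumptions not in the documents: normal test error with CV 3%, 5% or 8%, the 10% rule read as relative, and one follow-up test with the same CV.

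Apparent mean gain in subjects with no true change, minimum baseline:

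| Pre-dose tests | CV 3% | CV 5% | CV 8% |
|---|---|---|---|
| Two | 1.7% | 2.3% | 2.5% |
| Three | 2.6% | 3.9% | 5.6-5.7% |

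With the mean of the tests as baseline, the apparent gain is about 0.

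Share flagged as a fall above 15% at one visit, CV 5%, two tests, true level 80% predicted:

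| True fall | Lowest value | Mean of tests |
|---|---|---|
| None | 0.2% | 0.5% |
| 10% | 11% | 18% |
| 15% | 37% | 50% |
| 20% | 74% | 84% |
| 25% | 95% | 98% |

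Letting the true level vary between subjects (mean 85, SD 12) gives nearly the same: 36.9% against 50.6% for a true 15% fall, and 73.6% against 84.6% for a true 20% fall. In that setting, the lowest-value share for a true 15% fall is 33.9% at CV 3% and 41.6% at CV 8%, against 50.3-51.5% with the mean.

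With three tests at CV 5%, the lowest-value baseline flags 28% of true 15% falls and 65% of true 20% falls, against 50% and 86% with the mean.

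**The case against.** The rule is deliberate and pre-specified, and it buys specificity. A true 10% fall is below the threshold, so flagging it is an error, and the minimum does this less often (11% against 18% at CV 5%). With no change at CV 8%, the figures are 3.6% against 5.6%. This stands, and it belongs in the cost of any change. The 37% against 50% contrast also sits exactly at the threshold, where any unbiased baseline gives about half.

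A reader might infer that the rule hides lung toxicity. The documents do not support that. At CV 5% with two tests, most true 20% falls and nearly all true 25% falls are still flagged at one visit. The rule is the same in all arms, and the between-arm difference in mean change is not materially biased. SAP 4.10.5 sends persistent cases to the Safety Review Team (SRT) for final adjudication. Section 4.10.9 lists all pulmonary function results and plots individual DLCO profiles. Protocol 10.8.1 lets the DRC request individual data.

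A reader might also infer that DLCO alone departs from a uniform last-value rule. It does not: the other pulmonary function parameters follow the DLCO visit, and SAP 4.5.3 takes the worst-grade laboratory value when there are several at one visit.

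Nor do protocol and SAP contradict each other here. The protocol leaves baseline undefined, and further guidance sits in documents not available for this review.

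Finally, Day 1 alone is the noisier alternative. It flags 20% of true 10% falls and 82% of true 20% falls at CV 5%, so it is worse than the mean on both counts. What survives is a bias of known direction that existing data can remove.

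**Conclusion.** The point holds as attenuation. Following SAP 4.10.9 as written understates DLCO decline in its own tables, and in the 4.10.5 and DRC displays if they use the same baseline. The direction is certain; the size is not. It rests on an assumed CV of 3-8% that neither document gives. On that basis stable subjects appear to gain about 1.7-2.5% with two pre-dose tests. The 2.6-5.7% gain with three applies only to retested subjects, and no retest rate is stated. Falls near the threshold lose most in detection: about 13 percentage points for a true 15% fall and 10 for a true 20% fall, at CV 5% with two tests. No false signal arises, but the between-arm gap in event counts narrows when one arm truly declines. This is worth correcting because it is cheap, not because the plan would miss large falls.

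**What to change.** In SAP 4.10.9, define baseline DLCOHCPP as the mean of the valid pre-dose tests of the final screening period, and each other pulmonary function parameter as the mean of its own valid pre-dose tests. The second part also covers a visit with DLCO but no spirometry. Use this baseline for the change-from-baseline, >15% and DRC tables, and keep the lowest-value version as a sensitivity display.

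Reconcile the protocol's AESI and interruption passages with SAP 4.10.5 and 4.10.9 on which baseline is meant. This review takes no position on the clinical rule. While editing 4.10.5, also settle its label (>15%) against its definition (≥15%).

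The cost is wording in the SAP and DRC shells; no new tests are needed. The downside is more single-visit flags in subjects without a true fall above 15%. With no change, these are about 0.5% against 0.2% at CV 5% and 5.6% against 3.6% at CV 8%; with a true 10% fall at CV 5%, 18% against 11%. The three-week persistence requirement filters such flags from the persistent-event table but not from the by-visit table.

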#### **4.10.10 Vital Signs, Physical Findings and Other Observations Related to Safety**

The following vital signs will be assessed at screening, baseline, follow-up visit, early withdrawal-visit and several visits in between:

Temperature (in °C), systolic and diastolic blood pressure (mmHg), Heart rate (beats/min), respiration rate (breaths/min), weight(kg) and calculated BMI (kg/m^2).

Pregnancy testing must be carried out for women of childbearing potential and will consist of serum testing at Screening and urine testing every four weeks starting at Week 4 as well as urine testing at follow-up visit and early withdrawal-visit. Pregnancy test results will be listed only.

Physical examination will be performed at screening, baseline, follow-up visit, early withdrawal-visit and several visits in between. Findings will be assigned by investigator to medical history, adverse event or serious adverse events.

Subjects with findings or subjects who missed examinations will be shown in a listing.

The following summaries will be provided:

- A summary of each vital sign parameter by randomised treatment group and time point
- A summary of the change from Baseline in each vital sign parameter by randomised treatment group and time point.
- Boxplots of the change from Baseline in each vital sign parameter by randomised treatment group and time point.
- A summary of the number and percentage for history of tobacco use and family history of cardiovascular risk factors by randomised treatment group.

Triplet 12-lead ECGs will be obtained at screening, Week 12, 24, 52 and potential early withdrawal-visit. All ECG parameters will be calculated by taking the mean of the non-missing values obtained in the up to three 12-lead ECG evaluations at each visit.

The following summaries will be provided:

- A summary of each ECG parameter (i.e. heart rate, PR, QRS, QT, QTc) by randomised treatment group and time point
- A summary of the change from baseline in each ECG parameter by randomised treatment group and time point.

- A summary of the number and percentage of subjects with abnormal findings for each ECG parameter by randomised treatment group and time point.
- A summary of the number and percentage of subjects with QTc interval exceeding  $>450\text{ms}$  /  $>480\text{ms}$  /  $>500\text{ms}$  by randomised treatment group and time point.
- A summary of the number and percentage of subjects with change from baseline in QTcF interval exceeding  $>30\text{ms}$  /  $>60\text{ms}$  by randomised treatment group and time point.
- Boxplots of the change from baseline for each ECG parameter by randomised treatment group and time point.

By-subject listings of vital sign parameters, and ECG results (individual and average) and any other observations related to safety will be provided.

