#### 4.9.1.6 Examination of Subgroups

A subgroup analysis for subjects with early RA (i.e. < 2 years disease duration before first study medication administration) will be conducted if there are at least 10% subjects with early RA in the ITT population.

Additionally, subgroup analyses for selected endpoints may be conducted by gender if an adequate number of subjects are represented in each subgroup.

The following endpoints will be summarised for all subgroups in the same way as done for the entire population:

- DAS28(CRP) remission at all assessment points
- Change from Baseline in DAS28(CRP) at all assessment points
- ACR 20/50/70 response rates at all assessment time points

The following outputs for key safety endpoints will be provided by randomised treatment group for all subgroups:

- Overall summary of AEs
- Number and percentage of subjects reporting an AE by SOC and PT
- Number and percentage of subjects reporting a serious AE by SOC and PT
- Summary of AESIs
- Summary of subjects with pulmonary findings

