### **4.10 Safety Evaluation**

All safety summaries and analyses will be based upon the ITT population by actual treatment group at the time of safety event or assessment. Actual treatment group is either the randomised treatment group or “Rescued Subjects” for subjects who got escalated. Only assessments that happen after the administration of the first dose of rescue treatment will be assigned to the treatment group of “Rescued Subjects”.

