**Table 7 Adverse Events of Special Interest**

AESI	Programmatical Derivation
TP-GDO-WW-016-03 Effective Date: 26 Aug 15 Related to: SOP-GDO-WW-019	CONFIDENTIAL Project Document Version No. 2.0 Project Document Effective Date: Date of last signature Page 56 of 80

Serious infections, including serious respiratory infections.	SAEs, Filter on infections SOC
Opportunistic infections including TB reactivation	Opportunistic infections will be adjudicated by the SRT, using the preferred terms list given in Appendix A . Final adjudication conducted by SRT.
Neutropenia	Based on Grade 3 or 4 absolute neutrophil count
PAP (Pulmonary alveolar proteinosis)	If identified then list all AEs for those subjects.
Hypersensitivity reactions, including anaphylaxis	Hypersensitivity reactions will be adjudicated by the SRT, using AE data and data from hypersensitivity reactions eCRF page. Final adjudication conducted by SRT.
Injection site reactions	Using data from Injection site reactions eCRF page

AEs with missing intensity will be considered severe. AEs with missing relationship to study medication will be considered as related both to GSK3196165/Placebo and to MTX.

Where dates are missing or partially missing, adverse events will be assumed to be treatment-emergent, unless there is clear evidence (through partial dates as described in section 4.5) to suggest that the adverse event started prior to the first dose of study treatment or more than 12 weeks after the last dose of study treatment.

Adverse Events will be summarised by system organ class (SOC) and preferred term (PT). Summaries will provide the number of subjects reporting at least one AE and the total number of events reported.

The following summaries of AEs will be provided by actual treatment group at the time of the AE:

- Overall summary of AEs, including number and percentages of subjects with
  - Any AE
  - Serious AE
  - Discontinuation due to AE
  - Drug-related AE
  - AE leading to death
- Overall summary of Adverse Events
- Number and percentage of subjects reporting an Adverse Events
- Most common AEs (reported by >5% of the subjects in total)
- Plot of Most Common Adverse Events and Relative Risk
- Number and percentage of subjects reporting an Adverse Events by maximum intensity
- Number and percentage of subjects reporting an adverse events by relationship to study treatment

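### ECG, vital-sign and subgroup safety tables are specified by randomised group, against the SAP's own rule of actual treatment at the time of assessment

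*SAP*

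**What the plan says.** The general safety rule in SAP 4.10 is: "All safety summaries and analyses will be based upon the ITT population by actual treatment group at the time of safety event or assessment". It then defines the rescue group: "Only assessments that happen after the administration of the first dose of rescue treatment will be assigned to the treatment group of" rescued subjects. The adverse-event section (SAP 4.10.2) follows this: "The following summaries of AEs will be provided by actual treatment group at the time of the AE". The sections on serious adverse events, disease-related events and respiratory events (4.10.3 to 4.10.5) and the laboratory boxplots (4.10.8) do the same.

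Three places say otherwise:

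- SAP 4.10.10, which sits under 4.10, specifies "A summary of each vital sign parameter by randomised treatment group and time point" and "A summary of each ECG parameter (i.e. heart rate, PR, QRS, QT, QTc) by randomised treatment group and time point". The changes from baseline, the boxplots, the counts of QTc above 450, 480 and 500 ms, and the table that begins "A summary of the number and percentage of subjects with change from baseline in QTcF interval exceeding" 30 or 60 ms are all by randomised group too.
- SAP 4.9.1.6, on subgroups: "The following outputs for key safety endpoints will be provided by randomised treatment group for all subgroups". The list covers AEs, SAEs, AESIs and pulmonary findings.
- SAP 4.3 closes its population definitions by stating that all endpoints are analysed in the ITT population by randomised group, with no exception for safety.

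Neither SAP 4.10 nor SAP 4.14 (changes to the planned analysis) declares an exception.

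**The concern.** Subjects in every arm except 180 mg can be moved to 180 mg, or to the highest dose still open, from Week 14 (no EULAR response at Week 12) or from Week 26 (DAS28 above 3.2 at Week 24). After that, the randomised label no longer describes the drug being taken. A placebo subject who escapes at Week 14 and has a QTcF outlier at Week 24 is counted under placebo in the ECG table. If that subject has a post-rescue adverse event, a subgroup table shows it under placebo while the main AE table shows it under Rescued Subjects.

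Two things are at stake. Contrasts between active doses and placebo in these tables are pulled towards zero. The same event can also sit in different columns of one report. The study is meant to choose effective and safe doses for Phase 3, so dose attribution matters. Programmers also have two incompatible instructions for the same tables.

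**Working it through.** The documents give no figure to reproduce. The point rests on comparing the text; the arithmetic only sizes it.

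**1. Text side by side**

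| Output | SAP section | Column variable |
|---|---|---|
| All safety summaries (rule) | 4.10 | Actual treatment, plus Rescued Subjects |
| AE, SAE, AESI, disease-related and respiratory events | 4.10.2 to 4.10.5 | Actual |
| Vital signs and ECG, all summaries and boxplots | 4.10.10 | Randomised |
| Subgroup AE, SAE, AESI and pulmonary tables | 4.9.1.6 | Randomised |
| All endpoints (general statement) | 4.3 | Randomised |

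The SAP's intent elsewhere agrees with 4.10. SAP 4.2 sets period boundaries so that early adverse events are credited to the initial dose, and SAP 4.11.1.2 separates rescued subjects even for actigraphy.

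**2. Which data are affected**

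Scheduled ECGs after baseline are at Weeks 12, 24 and 52 (SAP 4.10.10). Week 12 precedes any rescue dose. Week 24 follows the first escape point and Week 52 follows both. Vital signs before the first rescue dose are correctly placed; later ones in escaped subjects are not. The subgroup tables mix events from before and after rescue.

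**3. How many subjects, at the first escape**

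Inputs: assumed Week 12 mean changes in DAS28(CRP) and SD 1.0 (SAP 4.13.2), 35 per arm (SAP 4.13.1), and the EULAR grid (SAP 3.2.1). I assume normally distributed changes and no dropout. An improvement of 0.6 or less is non-response at any current DAS28, so it gives a floor. An improvement of 1.2 or less would be non-response only if current DAS28 were above 5.1, so treating all such subjects as non-responders gives a ceiling.

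For mean improvement m:

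- Floor = Φ((0.6 − m)/SD)
- Ceiling = Φ((1.2 − m)/SD)

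For placebo at SD 1.0:

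- Floor = Φ(0.6 − 1.0) = Φ(−0.4) = 0.345; × 35 = 12.1
- Ceiling = Φ(1.2 − 1.0) = Φ(0.2) = 0.579; × 35 = 20.3

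| Arm | m | Floor (of 35) | Ceiling (of 35) |
|---|---|---|---|
| Placebo | 1.0 | 34.5% (12.1) | 57.9% (20.3) |
| 22.5 mg | 1.54 | 17.4% (6.1) | 36.7% (12.8) |
| 45 mg | 1.83 | 10.9% (3.8) | 26.4% (9.3) |
| 90 mg | 2.1 | 6.7% (2.3) | 18.4% (6.4) |
| 135 mg | 2.24 | 5.1% (1.8) | 14.9% (5.2) |
| All five | | 26.1 of 175 | 54.0 of 175 |

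The SAP's sensitivity tables (4.13.4) also use SD 0.7 and 1.3. The placebo floor is then Φ(−0.4/0.7) = 28.4% (9.9 of 35) and Φ(−0.4/1.3) = 37.9% (13.3 of 35).

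**4. Effect on a contrast**

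Let δ be the true Week 24 difference between 180 mg and placebo on an ECG or vital-sign measure, and s the share of the placebo arm already rescued. If rescued subjects show the same effect as the randomised 180 mg arm, the randomised-group table estimates (1 − s)δ. With s = 0.345 that is 0.655δ; with s = 0.284 it is 0.716δ.

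**The case against.** The strongest reply is that the safety evidence that matters most is already handled correctly. The major secondary safety endpoints are adverse events, infections and pulmonary events, and their main tables use actual treatment. SAP 4.10.2 also adds a table for the period up to Week 14 and exposure-adjusted rates by dose. ECG and vital signs are not among those endpoints or among the outputs listed for the Data Review Committee in SAP 4.10.11.1. The subgroup tables are conditional: early RA only if at least 10% of the ITT population qualifies, and gender only optionally. All of this stands and limits the reach of the point.

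A reader might infer that serious ECG findings on the top dose would be hidden under placebo. The documents do not support that. Protocol 5.4.2 makes QTc above 500 ms a withdrawal criterion (with separate thresholds for bundle branch block), Protocol 7.4.5 has clinically significant ECG abnormalities recorded as adverse events, and SAP 4.10.10 plans by-subject ECG listings. A case could be misplaced in one table, but it would be visible elsewhere.

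It can also be said that randomised groups preserve the randomised comparison and that SAP 4.3 supports them. The first part has force: columns split by rescue are selected on response, so actual-treatment tables do not give an unbiased comparison with placebo either. That argues for a labelled supplementary view. The second part does not settle the conflict, because SAP 4.3 read literally would contradict the main AE tables as well.

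**Conclusion.** The inconsistency is real and explicit, and no stated exception removes it. It is confined to post-rescue ECG and vital-sign data and to the conditional subgroup safety tables. On the SAP's own placebo mean, at least 34.5% of that arm (about 12 of 35) at SD 1.0, or 28.4% at SD 0.7, would sit under the wrong treatment at the Week 24 ECG. This assumes normal changes and no dropout; the dilution also assumes an equal effect after rescue. For 90 mg and 135 mg the floors are only 6.7% and 5.1%.

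A reader might go further and infer that the Week 52 placebo column would consist mostly of subjects on 180 mg. The documents cannot show that. The share escaping at Week 24 depends on baseline DAS28 and on the correlation between visits. Neither is given, and entry requires only a DAS28 of at least 3.2. Withdrawal at Week 38 of those without a Week 36 EULAR response would also change who remains at Week 52, and the escape dose need not be 180 mg if that arm has been closed.

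This should be fixed, but it does not threaten the main safety conclusions.

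**What to change.** - SAP 4.10.10: present post-baseline ECG and vital-sign summaries, outlier counts and boxplots by actual treatment group at the time of assessment, with a Rescued Subjects column. Keep randomised group for the tobacco and family-history table, which is a baseline display.
- SAP 4.9.1.6: make the same change for the safety outputs only.
- SAP 4.3: limit the closing statement to efficacy, or add a safety exception that points to 4.10.
- If a randomised-group view is wanted, keep it as a labelled supplement or cut it at the first rescue dose, and state the exception in 4.10.
- Check the laboratory listings (4.10.8) and the DLCO profile figure (4.10.9), which also use randomised group.

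The cost is SAP wording and a different column variable in a few tables, with no new data. The downside is that the post-rescue placebo and low-dose columns become smaller and are selected on response. At SD 1.0 and before dropout, at most about 23 of 35 placebo subjects (35 − 12.1 = 22.9) would remain at the Week 24 ECG. A footnote on these tables should say so.
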